Name of Principal Investigator:	
Name of Study Site:	
Location of Study Site:	
(City, region/province/state, country)	
Signature	Date (DD MMM YYYY)

SYNOPSIS

Name of Sponsor: ApoPh	arma Inc.	Individual Study Table Referring	(For National Authority	
Name of Finished Produc	et: Deferiprone	to Part of the Dossier Volume:	Use Only)	
Name of Active Ingredier dimethylpyridin-4-one	nt: 3-hydroxy-1,2-	Page:		
Title of study:		efficacy study of Ferriprox® for load in patients with sickle cell		
Study code:	LA38-EXT			
Phase of development:	Phase IV			
Objectives:	Objectives: Primary: To evaluate the long-term safety and tolerability of deferiprone in iron- overloaded patients with sickle cell disease or other anemias Secondary: To evaluate the efficacy of deferiprone in the treatment of iron overload in patients with sickle cell disease or other anemias who have received deferiprone for up to 3 years			
Study design:	LA38-EXT is a 2-year prospective, multi-center, single-arm, open-label extension of study LA38-0411. All patients who complete the earlier study will be offered the opportunity to continue in the extension study, with the final visit of LA38-0411 being Visit 1 of LA38-EXT. Patients who had been treated with deferiprone during LA38-0411 (Group 1) will continue to receive deferiprone for an additional 2 years, while those who had been treated with deferoxamine (Group 2) will be switched to deferiprone. Dosage will be 25–33 mg/kg three times a day (t.i.d.). All patients will visit the site quarterly for assessments of safety and efficacy for up to 2 years. Patients in Group 1 will additionally have blood counts monitored monthly, while those in Group 2 will have them monitored weekly for the first 6 months, biweekly for the next 6 months, and monthly thereafter.			
Duration of participation:	The duration of participation in the extension study for each patient (i.e., first visit to last visit) will be approximately 2 years.			
Criteria for evaluation: • Adverse events (AEs): Frequency, severity, time to onset, duration, relatedness to study product • Serious adverse events (SAEs): Frequency, severity, time to or duration, and relatedness to study product • Number of discontinuations due to AEs Efficacy: The time points for the efficacy assessments are defined below. Since the baseline measures are by definition those taken prior to the start of deferiproduct.		severity, time to onset, ed below. Since the		

Criteria for	therapy, "baseline" is defined differently for the two groups, as follows:
evaluation (cont'd):	• Group 1: For patients who received deferiprone in LA38-0411, the baseline visit of that study will be treated as the baseline visit of LA38-EXT as well. Thus, Week 0 of the extension study will be Year 1 (i.e., the completion of one year of deferiprone treatment), Week 52 will be Year 2, and Week 104 will be Year 3.
	• Group 2: For patients who received deferoxamine in LA38-0411, the start of the extension study (Week 0) will be treated as the baseline visit. For this group, therefore, Week 52 will be Year 1, and Week 104 will be Year 2.
	Efficacy endpoints are provided below. For Group 1, the change from baseline to Year 1 is derived from study LA38-0411. For Group 2, there is no Year 3 of deferiprone treatment.
	The change from baseline to Year 1 (both groups; Group 1 data are from LA38-0411), from baseline to Year 2 (both groups), and from baseline to Year 3 (Group 1 only) in liver iron concentration (LIC), as measured by magnetic resonance imaging (MRI)
	• The change from baseline to Year 1 (both groups; Group 1 data are from LA38-0411), from baseline to Year 2 (both groups), and (Group 1 only) from baseline to Year 3 in cardiac MRI T2*
	• The change from baseline to Year 1 (both groups; Group 1 data are from LA38-0411 data), from baseline to Year 2 (both groups), and from baseline to Year 3 (Group 1 only) in serum ferritin
	• Responder analysis, defined as the percentage of patients who show a ≥20% decline from baseline in LIC or serum ferritin or a ≥20% increase from baseline in cardiac MRI T2* at Year 1 (both groups; Group 1 data are from LA38-0411), at Year 2 (both groups), and at Year 3 (Group 1 only)
Number of patients:	In the LA38-0411 study, a planned total of 300 patients will be randomized to receive 1 year of treatment with either deferiprone or deferoxamine. All patients who complete that study will be invited to enroll in the extension study.
Main criterion for inclusion:	Completed study LA38-0411
Investigational product:	Product: Ferriprox® (deferiprone) 500 mg tablets or deferiprone 80 mg/mL oral solution Dose: 25–33 mg/kg t.i.d. Mode of administration: Oral
Schedule of treatment and specimen collection:	All patients will be scheduled to take deferiprone daily, 3 times a day, for up to 2 years. Safety and efficacy assessments will be conducted at the following time points: • Hematology: • Group 1: Monthly up to Visit 9 (End of Study) or the Early

Schedule of treatment and specimen collection (cont'd):

Termination visit

- Group 2: Weekly up to Visit 3 (Week 26), then biweekly up to Visit 5 (Week 52), then monthly up to Visit 9 (End of Study) or the Early Termination visit
- Biochemistry: Visit 1 and semi-annually up to Visit 9 or the Early Termination visit
- Serology: Visits 1 and 9
- Serum ferritin: Visit 1 and quarterly up to Visit 9 or the Early Termination visit
- Liver MRI scan: annually, at Visits 1, 5, and 9 or Early Termination visit
- Cardiac MRI T2* scan: annually, at Visits 1, 5, and 9 or Early Termination visit

Statistical methods:

Safety Analysis

The incidences of AEs and SAEs reported from the start of deferiprone therapy for all patients will be tabulated. For patients continuing on deferiprone, this time period will be from the start of LA38-0411 to the completion of LA38-EXT; while for those switching to deferiprone, it will be from the start of LA38-EXT to the completion of LA38-EXT. AEs will be summarized by worst severity and by relationship to the study medication. Time to onset and duration of all SAEs, of AEs of special interest such as neutropenia, agranulocytosis, increased ALT, and arthralgia, and of additional AEs that will be determined at the end of LA38-0411, will be analyzed as follows: 1) the mean time to the first onset and the mean time to the last recurrence will be calculated, and 2) the mean duration for the first episode and the mean duration for any recurrent episodes, excluding the first episode, will be calculated for all SAEs and such AEs.

The percentage of discontinuations due to AEs will be calculated, and the AEs leading to discontinuation will be summarized in a frequency table.

Laboratory data (hematology and chemistry) will be summarized using descriptive statistics for continuous variables and frequency tables for discrete variables. The incidences of out-of-range data that are seen for two consecutive measures will be tabulated, and the changes from baseline to the end of study will be presented in shift tables.

Efficacy Analysis

Changes in LIC, in cardiac MRI T2*, and in serum ferritin from baseline to Year 1(both groups; Group 1 data are from LA38-041), from baseline to Year 2 (both groups), and from baseline to Year 3 (Group 1 only) will be summarized with descriptive statistics, and will be tested against no change using a one-sample t-test. The changes in these 3 efficacy measures from the start of deferiprone therapy to the last visit of LA38-EXT in all patients, irrespective of whether deferiprone therapy was initiated in LA38-0411 or in LA38-EXT, will also be tested using a one-sample t-test. In addition, the percentages of responders will be tabulated for Year 1 (both groups; Group 1 data are from LA38-0411), for Year 2 (both groups), and for Year 3 (Group 1 only) of

	deferiprone therapy.
	Additional statistical analysis may be performed if deemed necessary. Details will be provided in the statistical analysis plan.
Version and date of the protocol:	Version 3.1, 01 MAY 2017

TABLE OF CONTENTS

S	GNATUF	RE PAGES	2
S	YNOPSIS		4
L	IST OF IN	N-TEXT TABLES	11
L	IST OF A	BBREVIATIONS AND DEFINITIONS OF TERMS	12
1	INT	RODUCTION	13
	1.1 Ba	ackground	13
	1.1.1	Sickle Cell Disease	13
	1.1.2	Ferriprox [®]	14
	1.2 Ra	ationale	15
	1.3 Po	otential Risks and Benefits	15
2	STU	DY OBJECTIVES	18
	2.1 Pr	imary Objective	18
	2.2 Se	econdary Objective	18
3	STU	DY DESIGN	18
	3.1 De	escription of Study Design	18
	3.2 Ra	ationale for Study Design	18
	3.3 Ra	ationale for Selection of Doses	18
4	STU	DY POPULATION	20
	4.1 N	umber of Patients	20
	4.2 In	clusion Criteria	20
	4.3 Ex	xclusion Criteria	20
	4.4 E1	nrolment Violations	21
	4.5 Pa	ntient Withdrawal	21
	4.5.1	Follow-up of Patient Withdrawal Due to Pregnancy	22
	4.5.2	Replacement of Patients Who Withdraw	23
	4.5.3	Treatment Interruptions	23
	4.6 Pr	ior and Concomitant Therapies	24
	4.7 Re	escue Medication	24
5	STU	DY PROCEDURES	24
	5.1 V	isit Procedures	27

	5.2	Method	d of Assignment to Treatment	39
	5.3	Blindir	ng Procedures	39
	5.4	Allocat	tion of Patient Numbers	39
	5.5	Treatm	ent Compliance	39
6	S	TUDY T	FREATMENTS	39
	6.1	Investi	gational Product	40
	6.1	1.1 Do	osage Form and Mode of Administration	40
	6.1	1.2 Pr	ecautions for Use	40
	6.2	Referei	nce Product	40
	6.3	Packag	ging and Labeling	40
	6.4	Shippii	ng and Storage	40
	6.5	Produc	t Accountability	40
	6.6	Replac	ement Doses	41
	6.7	Dispos	ition of Unused Product	42
	6.8	Other S	Study Supplies	42
7	N	MEASUI	REMENTS AND EVALUATIONS	42
	7.1	Efficac	y Measurements	42

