In the sickle cell centers of the Cardeza Foundation and Thomas Jefferson University Hospital, approximately 50% of the patients with SCD admitted to the hospital received an average of 10 units of RBCs per year; of these, 17% to 37% developed iron overload. Compared to the non-iron-overloaded group, the iron-overloaded patients with serum ferritin level >1,500 µg/L and transferrin saturation >50% had a higher incidence of painful episodes per year (64% vs. 38%), organ failure (71% vs. 19%), and mortality (64% vs. 5%). Patients who died had significantly higher mean levels of serum ferritin than those who survived (2379 versus 597 μg/L, p<0.05). The results of this study indicate that iron overload is a determinant of morbidity and mortality in adult patients with SCD. (9) Results from a natural history study demonstrated that the unadjusted death rate of transfused patients with SCD (7.0/100 person years) was even higher than in patients with thalassemia (2.2/100 person years). (11) Iron metabolism and trafficking in patients with SCD have some distinctive characteristics. The high levels of inflammatory cytokines in SCD may enhance macrophage/reticuloendothelial cell iron and/or renal cell iron retention. This makes tissues that retain iron different in SCD, and thus the organs that fail due to excess iron load in patients with SCD are somewhat different from those of patients with thalassemia. (12) Indeed, unlike thalassemia patients, cardiac iron overload is not frequently observed in patients with SCD. (13) Nonetheless, cardiac siderosis does occur in some SCD patients who have been transfused for more than 10 years. (14) Care for SCD now commonly uses transfusion, which potentially results in iron overload and necessitates chelation. (12)

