7.2 Safety Measurements

7.2.1 Adverse Events and Serious Adverse Events

7.2.1.1 Definition of Adverse Events

An adverse event (AE) is any untoward medical occurrence in a patient who is administered a pharmaceutical or other therapeutic product in a clinical study, not necessarily having a causal relationship with the product. An AE can therefore be any unfavorable and unintended sign, symptom, or disease temporally associated with the use of a product, whether or not considered related to that product.

AEs include:

- Exacerbation of a pre-existing illness, including acute episodes/crisis of a chronic underlying condition
- An increase in frequency or intensity of a pre-existing episodic event or condition
- A condition detected or diagnosed after study treatment administration, even though it may have been present prior to the start of the study
- A continuous persistent disease or symptom present at baseline that worsens following the start of the study
- Accidents (e.g., involving a motor vehicle)
- Reasons for changes in concomitant medication (type of drug and/or dose)
- Medical, nursing, or pharmacy consultation
- Admission to hospital and surgical operations
- Abnormalities in laboratory findings (e.g., clinical chemistry, hematology, urinalysis),
 ECG, or other assessments (e.g., vital signs) that are not part of a larger medical
 condition already recorded as an AE and which are judged by the investigator to be
 clinically significant. The investigator should exercise medical and scientific judgment in
 deciding whether an abnormal laboratory finding or other abnormal assessment is
 clinically significant.

AEs do not include:

- A pre-existing disease or condition present or detected at the start of the study that does not worsen
- Hospital admissions or surgical procedures that had been planned prior to enrolment into the study
- The disease or disorder being studied, or a sign or symptom associated with that disease or disorder, unless it has worsened
- An overdose of either the study treatment or concurrent medication without any signs or symptoms

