9 STATISTICAL ANALYSIS

9.1 Endpoints

9.1.1 Primary Endpoints

- Adverse events (AEs): Frequency, severity, time to onset, duration, and relatedness to study product
- Serious adverse events (SAEs): Frequency and relatedness to study product
- Number of discontinuations due to AEs

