Table 14.2.3.3 Change in serum ferritin for DFO+DFP group – Data from the extension study

		DFO+DFP	
	Visit	N Mean ± SD (Min, Max)	P-value (One sample T-test)
Change in serum ferritin (µg/L)	From Month 12 to Month 15	XXX XX.X ± XX.X (xx.x, xx.x)	0xxxx
	From Month 12 to Month 18	XXX XX.X ± XX.X (xx.x, xx.x)	0xxxx
	From Month 12 to Month 21	XXX XX.X ± XX.X (xx.x, xx.x)	0xxxx
	From Month 12 to Month 24	XXX XX.X ± XX.X (xx.x, xx.x)	0xxxx
	From Month 12 to Month 27	XXX XX.X ± XX.X (xx.x, xx.x)	0xxxx
	From Month 12 to Month 30	XXX XX.X ± XX.X (xx.x, xx.x)	0xxxx

		DFO+DFP	
	Visit	N Mean \pm SD (Min, Max)	P-value (One sample T-test)
	From Month 12 to Month 33	xxx xx.x \pm xx.x (xx.x, xx.x)	0.xxxx
	From Month 12 to Month 36	xxx xx.x \pm xx.x (xx.x, xx.x)	0.xxxx

Data source: 16.2.16 Listing of serum ferritin

Table 14.2.3.4 Responder analysis in serum ferritin as defined $\geq 20\%$ decline in serum ferritin from baseline.

	Treatment				P-value (Fisher's exact test)	
	DFP+DFP		DFO+DFP			
	N	n (%)	N	n (%)		
Year 1	xxx	xx (xx%)	xxx	xx (xx%)	0.xxxx	
Year 2	xxx	xx (xx%)	xxx	xx (xx%)	0.xxxx	
Year 3	xxx	xx (xx%)	xxx	xx (xx%)	0.xxxx	

Data source: 16.2.16 Listing of serum ferritin

Table 14.2.3.5 Responder analysis in serum ferritin defined as $\geq 20\%$ decline in serum ferritin from baseline for DFP+DFO group – Data from the extension study.

	Treatment	
	DFO+DFP	
	N	n (%)
Year 1	xxx	xx (xx%)
Year 2	xxx	xx (xx%)

Data source: 16.2.16 Listing of serum ferritin

Table 14.3.1.1 Overall summary of adverse events

	Treatment		P-value (Fisher's exact test)
	DFP+DFP	DFO+DFP**	
N	xxx	xxx	
Number of patients experiencing at least one AE	xx (xx%)	xx (xx%)	0.xxxx
Number of patients experiencing at least one severe AE	xx (xx%)	xx (xx%)	0.xxxx
Number of patients experiencing at least one serious AE	xx (xx%)	xx (xx%)	0.xxxx
Number of patients experiencing at least one related* AE	xx (xx%)	xx (xx%)	0.xxxx
Number of patient deaths	xx (xx%)	xx (xx%)	0.xxxx
Number of patient withdrawals due to AEs	xx (xx%)	xx (xx%)	0.xxxx

*Includes possibly, probably, and definitely related. Worst case scenario of causality between the investigator and company's assessment.

**AEs occurred while on DFP treatment.

Data source: 16.2.23 Listing of adverse events

Table 14.3.1.2 Adverse events

		Treatment		
		DFP+DFP (N=xxx)	DFO+DFP (N=xxx)	
Exposure (patient-years): x.xx		Exposure (patient-years): x.xx		
Total Events: xxx		Total Events: xxx		

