System Organ Class Preferred Term		n Patients (%)	n Patients (%)	P-value (Fisher's exact test)
CCCCCCC		x (x.x)	x (x.x)	0xxxx
Cccccc		x (x.x)	x (x.x)	0xxxx
Ccccccc		x (x.x)	x (x.x)	0xxxx
Ccccccc		x (x.x)	x (x.x)	0xxxx
.....	

Note: Similar tables will be produced from Table 14.3.1.3 to Table 14.3.1.7

Data source: 16.2.23 Listing of adverse events

Table 14.3.1.8 Adverse events by causality

		Treatment	
		DFP+DFP (N=xxx)	DFO+DFP (N=xxx)
System Organ Class Preferred Term	Relatedness (worst case)	Patients reporting (n=xx)	Patients reporting (n=xx)
CCCCCCCC		x (x.x)	x (x.x)
cccccc	Not Related*	x (x.x)	x (x.x)
	Related**	x (x.x)	x (x.x)
cccccc	Not Related	x (x.x)	x (x.x)
	Related*	x (x.x)	x (x.x)
.....

*Not related

**Possibly, Probably, or Definitely Related

Data source: 16.2.23 Listing of adverse events

Table 14.3.1.9 Time to the first onset of SAEs

	Treatment				
	DFP+DFP		DFO+DFP		
SAE	N	Mean ± SD (Min, Max)	N	Mean ± SD (Min, Max)	P-value (T-test)
Ccccccc	XXX	xx.x ± xx.x (xx, xx)	XXX	xx.x ± xx.x (xx, xx)	0xxxx
Ccccccc	XXX	xx.x ± xx.x (xx, xx)	XXX	xx.x ± xx.x (xx, xx)	0xxxx
....	XXX	xx.x ± xx.x (xx, xx)	XXX	xx.x ± xx.x (xx, xx)	0xxxx
Ccccccc	XXX	xx.x ± xx.x (xx, xx)	XXX	xx.x ± xx.x (xx, xx)	0xxxx

Note: Similar table will be produced for Table 14.3.1.10.

Data source: 16.2.23 Listing of adverse events

Table 14.3.1.11 Time to the last recurrence of SAEs

	Treatment				
	DFP+DFP		DFO+DFP		
SAE	N	Mean ± SD (Min, Max)	N	Mean ± SD (Min, Max)	P-value (T-test)
Ccccccc	XXX	xx.x ± xx.x (xx, xx)	Xxx	xx.x ± xx.x (xx, xx)	0xxxx
Ccccccc	XXX	xx.x ± xx.x (xx, xx)	Xxx	xx.x ± xx.x (xx, xx)	0xxxx
....	XXX	xx.x ± xx.x (xx, xx)	Xxx	xx.x ± xx.x (xx, xx)	0xxxx
Ccccccc	XXX	xx.x ± xx.x (xx, xx)	Xxx	xx.x ± xx.x (xx, xx)	0xxxx

Note: Similar table will be produced for Table 14.3.1.12.

Data source: 16.2.23 Listing of adverse events

Table 14.3.1.13 Duration of the first onset of SAEs

		Treatment			
		DFP+DFP		DFO+DFP	
SAE	N	Mean \pm SD (Min, Max)	N	Mean \pm SD (Min, Max)	P-value (T-test)
Ccccccc	XXX	XX.X \pm XX.X (xx, xx)	XXX	XX.X \pm XX.X (xx, xx)	0.xxxx
Ccccccc	XXX	XX.X \pm XX.X (xx, xx)	XXX	XX.X \pm XX.X (xx, xx)	0.xxxx
....	XXX	XX.X \pm XX.X (xx, xx)	XXX	XX.X \pm XX.X (xx, xx)	0.xxxx
Ccccccc	XXX	XX.X \pm XX.X (xx, xx)	XXX	XX.X \pm XX.X (xx, xx)	0.xxxx

Note: Similar table will be produced for Table 14.3.1.14.

Data source: 16.2.23 Listing of adverse events

Table 14.3.1.15 Duration of the last recurrence of SAEs

		Treatment			
		DFP+DFP		DFO+DFP	

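### AE frequency is a primary endpoint, but each preferred term is reported only as patients with at least one event, which compresses differences in recurrent events over 2 to 3 years

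*Protocol*

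**What the plan says.** Protocol section 9.1.1 lists as a primary endpoint "Adverse events (AEs): Frequency, severity, time to onset, duration, and relatedness to study product". SAP section 6.1.1 repeats this and defines time to onset and duration, but not frequency. SAEs are also to be described by frequency.

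The analysis text (Protocol Synopsis and section 9.4.1.4; SAP section 6.3.4) speaks of incidences: "The incidences of AEs and SAEs reported from the start of deferiprone therapy for all patients will be tabulated". That sentence does not settle whether patients or events are counted. The shells in SAP section 17 do:

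- Table 14.3.1.1 has rows such as "Number of patients experiencing at least one AE".
- Table 14.3.1.2 gives patients and percent in every system organ class and preferred-term row, with Fisher's exact test. The note below it says "Similar tables will be produced from Table 14.3.1.3 to Table 14.3.1.7", so common AEs, adverse drug reactions, SAEs and serious adverse drug reactions share the layout.
- Table 14.3.1.8, by causality, also counts patients.
- "Total Events: xxx" and a patient-years figure stand once per group in the header of Table 14.3.1.2.
- Tables 14.3.1.9 to 14.3.1.16 give time to first onset, time to last recurrence, and durations, for SAEs and AEs of special interest only.

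Protocol section 7.2.1.1 counts acute crises of a chronic condition as AEs, and also "An increase in frequency or intensity of a pre-existing episodic event or condition". Section 7.2.1.2 adds that AEs and SAEs related to the underlying condition are recorded separately from the others.

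**The concern.** A patient with one episode of a term and a patient with twelve contribute the same to a preferred-term row. From the header one can derive a rate for all AEs combined, but not for any single term. The recurrence tables say when the last episode came and how long episodes lasted, not how many there were.

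This is separate from unequal follow-up. Even if every patient were followed equally long, an ever/never percentage approaches its ceiling as follow-up lengthens, so a given relative difference in rate shows as an ever smaller difference in percentage. The study follows patients on deferiprone for up to 2 or 3 years, in a disease with recurrent morbidity. If the rate of a recurrent event differed between groups or changed over time, the planned tables would show it with less sensitivity than the recorded data allow.

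**Working it through.** The documents state no expected AE rate, precision or power, so there is no planned figure to reproduce.

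**Inputs from the documents.** Protocol section 1.2 plans 300 patients at 2:1, so at most about 200 in Group 1 (up to 3 years on deferiprone) and 100 in Group 2 (up to 2 years). Actual enrolment is not stated.

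**Assumptions.** Episode rate *m* = 0.5, 1 or 2 per patient-year. Counts vary between patients as gamma-Poisson with k = 1. There is no dropout, and the baseline rate is treated as known.

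**Formulas.** With mean count L = mT:

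- Share with at least one event: p = 1 − (1 + L/k)^(−k). For k = 1 this is L/(1 + L).
- SE of the percentage: √(p(1 − p)/n).
- SE of the mean count: √((L + L²/k)/n).
- Both SEs are taken at the raised rate.

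**Group 1 (n = 200, T = 3), rate 50% higher.**

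| m | Share before → after | Change (points) | SEs on percentage | SEs on event rate |
|---|---|---|---|---|
| 0.5 | 60.0 → 69.2% | 9.2 | 2.8 | 3.9 |
| 1 | 75.0 → 81.8% | 6.8 | 2.5 | 4.3 |
| 2 | 85.7 → 90.0% | 4.3 | 2.0 | 4.5 |

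Example, m = 1: L rises from 3 to 4.5. The percentage gives 0.0682/√(0.818 × 0.182/200) = 0.0682/0.0273 = 2.5. The rate gives 1.5/√((4.5 + 20.25)/200) = 1.5/0.352 = 4.3.

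**Group 1, rate doubled.** The share moves from 60.0 to 75.0%, 75.0 to 85.7% and 85.7 to 92.3%. These are changes of 15.0, 10.7 and 6.6 points, or 4.9, 4.3 and 3.5 SEs on the percentage. On the event rate the same doubling is 1.5/√(12/200) = 6.1, 3/√(42/200) = 6.5 and 6/√(156/200) = 6.8 SEs.

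**Group 2 (n = 100, T = 2), rate 50% higher.** The share moves from 50.0 to 60.0%, 66.7 to 75.0% and 80.0 to 85.7%.

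- Percentage: 0.100/√(0.24/100) = 2.0, 0.0833/√(0.1875/100) = 1.9 and 0.0571/√(0.1224/100) = 1.6 SEs.
- Event rate: 0.5/√(3.75/100) = 2.6, 1/√(12/100) = 2.9 and 2/√(42/100) = 3.1 SEs.

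**Sensitivity to heterogeneity.** With no heterogeneity (Poisson, p = 1 − e^(−L)) over 3 years, a doubling shows as follows:

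| Base rate per year | Share before → after | Change (points) |
|---|---|---|
| 0.25 | 52.8 → 77.7% | 24.9 |
| 0.5 | 77.7 → 95.0% | 17.3 |
| 1 | 95.0 → 99.8% | 4.7 |
| 2 | 99.8 → 100.0% | 0.2 |

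The last two changes are taken before rounding. Compression is thus severe at about 1 per year and above with little heterogeneity, and mild at low rates.

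**The planned between-group test, follow-up set equal at 2 years** (200 vs 100, one group at double the rate, two-sided 0.05, Fisher's test by exact enumeration). Power is 97% (Poisson) or 66% (k = 1) at 1 per year, and 1% or 47% at 2 per year. A Wald test on the log rate ratio has power above 99% in all four cases.

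**The case against.** Several points on the other side are sound.

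- **A reader might infer that a large rise would be nearly invisible.** The figures do not support that in general. Under the k = 1 model a doubling is 3.5 to 4.9 SEs on the percentage, and at 0.25 to 0.5 per year (Poisson, 3 years) it shows as 17 to 25 points. The description fits only high rates with little heterogeneity.
- **A reader might infer that the tables contradict the primary endpoint.** They do not. Frequency is undefined, and patient incidence is a permissible reading, consistent with the wording of the analysis text. The point is insensitivity, not contradiction.
- **A reader might take painful crises as the sure example.** Section 7.2.1.2 records disease-related events separately. The SAP lists medical events (16.2.22) apart from adverse events (16.2.23) without saying which holds crises. Section 7.2.1.1 includes acute crises but also excludes signs of the studied disease that have not worsened. The 64% versus 38% for painful episodes in the Protocol's background is a percentage and may itself be a share of patients.
- **There is no concurrent control.** Everyone takes deferiprone, so no summary can show a rise caused by the drug against a known baseline. A difference is visible only between groups or over time, and the SE figures above are best-case comparisons of two measures.
- **Part of the need is met.** The header gives an all-AE rate, the recurrence tables have an N column, all events are listed, and SAP section 14 allows more tables. None of this plans an event count or rate for a single term.

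**Conclusion.** The concern holds as a loss of sensitivity. For each preferred term the plan reports only whether a patient ever had the event, so no planned table shows how often the term recurs, although frequency is a primary endpoint and the events are recorded.

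Across the assumed rates, with k = 1, a 50% difference carries 2.0 to 2.8 SEs on the percentage and 3.9 to 4.5 on the rate in Group 1, and 1.6 to 2.0 against 2.6 to 3.1 in Group 2. The rate is the more sensitive measure in every case computed. The size of the gap rests on assumed rates and dispersion, on planned maximum numbers with full follow-up, and on a baseline treated as known. The documents do not establish that the primary safety question would go unanswered, or that crises are among the terms affected. This is an inexpensive improvement worth making before the tables are produced.

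**What to change.** 1. In SAP section 6.1.1, define frequency as both patients (%) and events.
2. In SAP section 6.3.4 and Tables 14.3.1.2 to 14.3.1.7, keep the number and percentage of patients. For each preferred term add the number of events, counting recurrences, and the events per 100 patient-years on deferiprone. Give a 95% CI that allows for clustering within patients: negative binomial with a log-exposure offset, or a robust variance.
3. State whether the events recorded separately under Protocol section 7.2.1.2, including crises, are held in listing 16.2.22 or 16.2.23, and apply the same event-rate summary to them.

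The cost is SAP wording and extra columns from events and exposure already collected. The tables become wider, and a few patients with many episodes can influence a rate. The clustering-robust interval makes that uncertainty visible, and the patient percentage beside it helps the reader judge it.
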